Outcomes:

3. Social Skills Improvement System (SSIS) to measure change in student disruptive behavior problems (Student Level Component) The effect statistic showing change in teacher-reported problem behavior exhibited by the sustainment focal student sample from Fall (SU1) to Spring (SU4) of the sustainment year. Student disruptive behaviors will be measured by the Social Skills Improvement System (SSIS) total problems scale.
4. Social Skills Improvement System (SSIS) social skills scale to measure change in student prosocial behavior (Student level component) The effect statistic showing change in teacher-reported social skills exhibited by the focal student sample (78 enrolled) from Fall (SU1) to Spring (SU4) of the sustainment year. Student prosocial behaviors will be measured by the Social Skills Improvement System (SSIS) social skills scale.

Leadership

Drs. [name] and [name] will provide oversight of the entire project including the development and implementation of project policies, procedures, and processes. Both Drs. [name] and [name] will share equal responsibility for implementation of the Scientific Agenda, the Leadership Plan, and the Specific Aims of the proposed project. Additionally, the MPIs will be responsible for ensuring that systems are in place to adhere to US Laws and NIH policies including human subject research, data, and facilities. Drs. [name] and [name] will share responsibility for all components of the proposed project. They will share equal responsibility for implementing the procedures related to participant recruitment and retainment for all Aims. [name] will be primarily responsible for coding procedures

and management (both treatment integrity and qualitative), data management, and overseeing the training and monitoring of the coding teams. [name] will be primarily responsible for community engagement and data collection. Finally, [name] will serve as contact PI and will assume fiscal and administrative management, responsibility for communication with NIH, and submission of annual reports.

Methodology Drs. [name] and [name] will lead the methodology team. The team will be comprised of Drs. [name], [name], and [name]. Drs. [name], [name], and [name] are experts in the methodological and statistical approaches employed in the proposed study. [name] will provide expert consultation on data analysis (e.g., how to address nesting), and interpretation for all Aims. The team will meet weekly throughout the duration of the project.

Data Analysis Strategy

Overview. The multilevel, interrupted time series design leverages an ongoing RCT, the BEST in CLASS Elementary Trial, to inform the development of a sustainment strategy for EBPs in school settings. The strategy will be based on key targets empirically identified by the project, specifically, the malleable features of BEST in CLASS, teachers, or schools that are associated with treatment fidelity and modifications to BEST in CLASS. A notable strength is that the teacher, intervention, and school targets have two relevant “baselines”: one from the implementation phase and one from the sustainment phase. Thus, the sustainment strategy will target influential factors from the start of sustainment and factors from the start of implementation that predicted later sustainment. The design is straightforward, but the analyses have a few complexities that require consideration. As detailed next, the complexities are readily addressed by the proposed analyses.

Data structure. As is common for implementation and sustainment research, the data are nested. In the proposed models, nesting will be addressed using two simultaneous strategies. The first is to use standard mixed-effects regression models, for example, for the nesting of repeated measurements within children, repeated measurements within teachers, children within teachers. The second strategy addresses nesting when the number of upper-level units is too small for accurate estimates of random effects. This approach, which will apply to the nesting of teachers within schools and schools within research sites, uses fixed effect indicators to control for systematic differences across nesting units. The combined approach is highly flexible, readily implemented, and ensures accurate estimates for key model parameters. The specific data structures vary across Aims 1 and 2, and as such, they are detailed separately below.

Modeling building, estimation, and significance testing. The mixed-effects regression models will be implemented using the lme4 package in R software. All outcomes are continuous, though the distributions will be inspected and confirmed prior to modeling. Should non-linear sampling distributions be required (e.g., Bernoulli, negative binomial, ordinal), the models will be implemented using adaptive quadrature in SuperMix. Significance testing will be based on the Wald test statistic, and 95% CIs will be computed to gauge the magnitude and precision of all effects. Planned contrasts will be specified using R’s multcomp package to obtain all comparisons of interest. Across Aims, dummy-coded fixed effect indicators will be included for schools and sites. Also, the models will include teacher-level indicators to control for systematic differences by grade. For each predictor of interest, prior to modeling, the level of measurement will be carefully considered, and ICCs will be computed to confirm the appropriate level(s) for scoring and modeling. To aid interpretation, each baseline factor will be centered around its grand mean prior to model entry.

Evaluation of Specific Aims

Aim 1. Determine if malleable baseline factors predict treatment fidelity and modifications to BEST in CLASS during implementation or sustainment. The outcomes for Aim 1—treatment fidelity (TIES Adherence and Competence Scales) and fidelity-consistent modifications (TIES Adherence

and Competence “Purity” Scales; are structured with four repeated measurements (level-1) nested within two phases (level-2; i.e., implementation phase, sustainment phase) nested within teachers (level-3). This is possible because all teachers have repeated measurements in both phases, permitting a single, simultaneous model to test (1) associations within the implementation phase, (2) associations within the sustainment phase, and (3) differences in associations across phases. Fixed effect indicators will control for differences by schools, sites, and grades, and a dummy-coded indicator will differentiate measurements in the implementation and sustainment phases. Change over time will be modeled according to linear and quadratic (if indicated) polynomials. The focal predictors are malleable baseline factors, including teacher (self-efficacy, burnout, attributions), intervention (usability), and school (climate, classroom atmosphere, classroom adversity) factors. For each predictor, there are two scores: a baseline score from the implementation phase and a baseline score from the sustainment phase. The model will necessarily exclude a main effect for the sustainment baseline score because it cannot predict the prior implementation phase outcomes (i.e., the reference phase). However, implementation baseline scores will be considered as predictors of outcomes across both the implementation and sustainment phases. The results will identify key factors that at the start of implementation or the start of sustainment were predictive of sustainment outcomes. The results will inform development of the sustainment strategy. Of note, standard formulations of models for discontinuous and piecewise change can be used to provide more targeted tests for change across the two phases. For example, this could test whether treatment fidelity and modifications to BEST in CLASS change during implementation, whether the overall levels differ for implementation and sustainment, and whether the slope for sustainment differs from the slope for implementation.

Aim 2. Determine if treatment fidelity or modifications to BEST in CLASS predict child outcomes during implementation or sustainment. The outcomes for Aim 1—treatment fidelity (TIES Adherence and Competence Scales) and modifications to BEST in CLASS (TIES Adherence and Competence “Purity” Scales;)—are structured with four repeated measurements (level-1) nested within two phases (level-2; i.e., implementation phase, sustainment phase) nested within teachers (level-3). This is possible because all teachers have repeated measurements in both phases, permitting a single, simultaneous model to test (1) associations within the implementation phase, (2) associations within the sustainment phase, and (3) differences in associations across phases. Fixed effect indicators will control for differences by schools, sites, and grades, and a dummy-coded indicator will differentiate measurements in the implementation and sustainment phases. Change over time will be modeled according to linear and quadratic (if indicated) polynomials. The focal predictors are malleable baseline factors, including teacher characteristics (self-efficacy, burnout, attributions), intervention characteristics (usability), and school characteristics (climate, classroom atmosphere, classroom adversity). For each predictor, there are two scores: a baseline score from the implementation phase and a baseline score from the sustainment phase. The model will necessarily exclude a main effect for the sustainment baseline score because it cannot predict the prior implementation phase outcomes (i.e., the reference phase). However, implementation baseline scores will be considered as predictors of outcomes across both the implementation and sustainment phases. The results will identify key factors that, at the start of implementation and/or the start of sustainment, were predictive of sustainment outcomes. The results will inform development of the sustainment strategy.

Of note, standard formulations of models for discontinuous and piecewise change can be used to provide more targeted tests of change in outcomes across the two phases. For instance, a two-level model with eight repeated measurements (level-1; four per phase) nested within teachers (level-2), an overall slope term, a phase indicator, and a slope term from the start of sustainment could test whether treatment fidelity and modifications change during implementation, whether the overall levels differ for implementation and sustainment, and whether the slope for sustainment differs from the slope for implementation. Alternatively, each outcome could be evaluated in a separate model for the implementation and sustainment phases, where the structure would reduce to two levels (i.e., repeated measurements within teachers).

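### Omitting the main effect of the sustainment-start score makes its Aim 1 coefficient an association net of implementation fidelity, not the within-sustainment association the plan sets out to test

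*Combined protocol and SAP*

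**What the plan says.** The combined protocol and SAP, under Evaluation of Specific Aims, Aim 1, describes the fidelity outcomes as "four repeated measurements (level-1) nested within two phases (level-2; i.e., implementation phase, sustainment phase) nested within teachers (level-3"), and says that "a dummy-coded indicator will differentiate measurements in the implementation and sustainment phases". One simultaneous model is meant to test three things: ("1) associations within the implementation phase, (2) associations within the sustainment phase, and (3) differences in associations across phases".

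Each baseline factor has two scores, one from the start of each phase. They are treated differently. On the one hand, "implementation baseline scores will be considered as predictors of outcomes across both the implementation and sustainment phases". On the other, "The model will necessarily exclude a main effect for the sustainment baseline score because it cannot predict the prior implementation phase outcomes (i.e., the reference". The stated use is: "The results will identify key factors that at the start of implementation or the start of sustainment were predictive of sustainment outcomes". The Data Analysis Strategy overview likewise builds the sustainment strategy on factors from both starting points.

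The same rule is repeated under the Aim 2 heading. The closing paragraph there says that each phase could be modelled separately, with repeated measurements within teachers. This is offered as an alternative, without a rule for choosing it and without any link to the sustainment-start scores.

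**The concern.** The reason given for the exclusion is about causal order: a score taken later cannot cause earlier fidelity. A regression constraint is about association. Self-efficacy, burnout or perceived usability scored after the implementation year can correlate with that year's fidelity, either because both reflect a stable teacher trait or because the year shaped the score. Omitting the main effect in a model whose reference phase is implementation asserts that this correlation, given the implementation-start score, is exactly zero.

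If the phases were modelled independently, a wrong zero in one would do no harm in the other. Here they are tied together by the teacher random effect, so the misfit carries over into the sustainment coefficient. At stake is the selection of targets for the sustainment strategy: a sustainment-start score can look weaker than its within-phase association, or can appear with the opposite sign.

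**Working it through.** **Inputs from the documents.** 52 teachers (Aim 1 outcomes); four measurements in each of two phases; implementation as reference; Wald tests with 95% CIs (two-sided 5% inferred). The plan gives no ICC, effect size or power for Aim 1, so there is no figure to reproduce.

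**Inferred.** No equation is printed. Because results are promised for sustainment-start scores while their main effect is excluded, the score must enter through its product with phase. Write X1 and X2 for the implementation-start and sustainment-start scores. The model is then: phase, X1, X1 × phase, X2 × phase, with teacher and phase-within-teacher random effects.

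**Assumed.** ρ (correlation of a teacher's two phase means, given the scores) of 0.3, 0.5 or 0.7; correlation of X1 with X2 of 0.5, both with SD 1; residual SD of a phase mean 1; no school, site, grade or time terms.

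**Algebra.** With balanced data the model reduces to two phase means per teacher:

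- implementation: Y1 = a1 + c1·X1 + g·X2 + e1
- sustainment: Y2 = a2 + c2·X1 + b2·X2 + e2, with corr(e1, e2) = ρ

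The planned model sets g = 0. Its X2 coefficient is then in effect the X2 slope in a regression of Y2 − ρ·Y1 on X1 and X2, which is **b2 − ρg**. When b2 = g this equals b2(1 − ρ). It is negative when b2 < ρg (for positive g), and equals b2 when g = 0 or ρ = 0. X1's sustainment coefficient gains ρ·g·δ, where δ is the slope of X2 on X1. With ρ = g = δ = 0.5 that is 0.5 × 0.5 × 0.5 = 0.125.

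For g = b2 = 0.5 the formula gives 0.5 × 0.7 = 0.35, 0.5 × 0.5 = 0.25 and 0.5 × 0.3 = 0.15. Simulated values are slightly lower because the misfit inflates the fitted ρ to 0.322/0.526/0.724. Using those values: 0.5 − 0.322 × 0.5 = 0.339, then 0.237 and 0.138.

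**Simulation (REML, 52 teachers, at least 1,000 data sets per setting).** The comparator is the model with the X2 main effect, reporting main effect plus interaction. The sustainment-phase-only model gives the same estimate.

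| Setting | ρ | Planned | Comparator |
|---|---|---|---|
| g = b2 = 0.5, mean slope | 0.3 / 0.5 / 0.7 | about 0.33 / 0.23 / 0.13 | about 0.50 |
| g = b2 = 0.5, power | 0.3 / 0.5 / 0.7 | about 53 / 36 / 18–22% | 82–84% |
| g = 0.3, b2 = 0, rejection | 0.3 / 0.5 / 0.7 | about 10 / 20 / 44%, mean slope negative | about 5% |
| g = 0.5, b2 = 0.1, mean slope | 0.3 / 0.5 / 0.7 | −0.06 / −0.16 / −0.27 | about 0.10 |
| g = 0, b2 = 0.5, power | 0.3 / 0.5 / 0.7 | 87 / 93 / 98%, no bias | 83–84% |

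A full eight-measurement, three-level fit with time terms (600 teachers, ρ = 0.5, g = b2 = 0.5) gave 0.28 as planned against 0.52 with the main effect, so the result is not an artefact of using phase means.

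**The case against.** A reader might infer that the plan will miss stable predictors. The documents do not support that for the factor as a whole. The implementation-start score remains a predictor of both phases, the strategy may draw on either score, and part of the association lost from one moves to the other. When both scores are noisy measures of one stable trait, the chance that at least one is significant for sustainment was 24/36/47% as planned against 25/36/47% with the main effect (ρ 0.3/0.5/0.7). What stands is that the power loss belongs to the sustainment-start coefficient, so the timing of a factor can be misattributed.

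A reader might also infer that false reversed associations are the usual result. They need b2 < ρg. A score that merely reflects observed implementation fidelity has b2 = ρg, and its planned coefficient is near zero (simulated −0.008/0.002/0.004), not reversed. In that case it is the within-phase slope that is non-zero (0.145/0.247/0.349), and it would flag a score that is only a consequence of earlier fidelity.

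It follows that association net of earlier fidelity is a defensible basis for choosing malleable targets. That is correct, but the plan does not name it as the target. It names the association within sustainment, and it justifies the exclusion by time order.

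Finally, the model is partly inferred, and ρ and the slopes are assumptions. This limits the percentages, not the direction of the algebra. The optional separate-phase models would avoid the problem, but the plan does not commit to them.

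**Conclusion.** The concern holds in a limited form. The exclusion is presented as necessary and is not. If the sustainment-start score is related to implementation fidelity given the implementation-start score, and a teacher's phases are correlated, its coefficient answers a different question from the one Aim 1 states. With equal slopes in both phases it is shrunk by a factor of about 1 − ρ; with a sustainment slope below ρg it changes sign. If either condition fails there is no bias, and the planned model is the more precise one. The figures show direction and range only: they rest on assumed ρ and slopes, and on an X2 × phase term inferred from the text. They do not show that factors will be lost from the sustainment strategy, or that reversed findings are to be expected in general.

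**What to change.** Under Aim 1, delete the rule excluding the main effect. State that each sustainment-start score's within-sustainment association will be estimated and tested in the two-level model of sustainment-phase measurements that the closing paragraph under Aim 2 lists as an option, and make this the stated analysis for these scores. Equivalently, keep the joint model, include the main effect as a nuisance term, and report main effect plus interaction. If association net of implementation fidelity is also wanted for choosing targets, name it as a separate estimand and report the planned coefficient under that label. Change the duplicate under the Aim 2 heading consistently; it is Aim 1 text.

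The cost is a few sentences and one simple model per score and outcome, with no new data. Where the zero constraint is true, the standard error grows by about 1/√(1 − ρ²): 1/√0.91 = 1.05, 1/√0.75 = 1.15 and 1/√0.51 = 1.40 at ρ of 0.3, 0.5 and 0.7. The plan should also say that the within-phase association is not to be read causally, since it can flag a score that only reflects earlier fidelity.
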